11.2 Ophthalmic Exam Findings

In addition to reporting of ocular AEs as above, numbers and proportions of participants in each study arm (if any) who had loss of best corrected vision in either eye by one line or more, compared to best corrected vision prior to treatment, at 6-month and 1-year evaluations will be reported. These numbers

will also be reported using eyes as numerator and denominator.

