Surgeons will administer the first dose of masked study drug (placebo or pAF fluid) directly after surgery, the morning of day 1, and three more times that day. Patients will then administer drops four times a day total for the next 6 days, for a total of 7 days of study drug administration. The patients will begin filling out the pain survey the night of day 1.

At a designated time on day 1 (2nd visit post-surgery), 3, 4, 5, 6, 7, and 8 each patient will be examined by one of the study investigators who will be masked to the drop regimen. The investigator will grade the size of the epithelial defect on day 1(AM), 3, 4, 5, 6, 7, and 8 by measuring the largest horizontal and vertical meridians using slit lamp biomicroscopy. If a patient has re-epithelialized by an earlier exam day (i.e., day 3) they will be able to skip all subsequent in person examinations except for day 8 (i.e., skip days 4, 5, 6, and 7). All patients will still need to record their pain rating scale at the end of each day and return for the day 8 visit.

The study investigators will be masked to which drop is being used for each patient. Patients will be required to store all drops in the freezer and will be masked as to which type of drop is being used.

Patients will also be seen at post-operative months 1, 3, 6 and 12. At each of these visits visual acuity and manifest refraction will be checked, along with a measure of ocular surface staining and corneal regularity. These are all standard procedures performed for post-operative PRK patients regardless of study participation.

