5.4 Assessment of Primary Endpoint(Safety)

Safety and tolerability will be evaluated by the PI from the findings of scheduled eye examinations at days 1 (day of surgery) through 8 (in-person follow-up visit) and at months 1, 3, 6 and 12 after initiation of pAF therapy. More frequent safety evaluations may be performed if clinically indicated or at the discretion of the investigator. Information from the eye examination at these additional safety evaluations will be collected and entered into the EDC as adverse events as appropriate.

All ocular adverse events will be recorded from randomization through Month 12. Any events that occur from time of consent to randomization will be recorded as medical history.

6 Safety Monitoring

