6.1.9 Follow-up of Serious, Unexpected and Related Adverse Events

All serious, unexpected and related adverse events, that are unresolved at the time of the patient's termination from the study, will be followed by the site investigators until the events are resolved, subject is lost to follow-up, the adverse event is otherwise explained or has stabilized, or 12 months have passed from the time of last study dose.

7 Assessment of secondary endpoints

1. Re-epithelialization will be graded by trained, masked examiners on days 1, 3, 4, 5, 6, 7, and 8 unless patient re-epithelializes sooner in which case they can skip visits until day 8. Dimensions of the epithelial defects will be directly measured using slit lamp bio-microscopy. The baseline epithelial defect will be measured by surgeons on Day 1 at the time of surgery. Examiners will be masked as to which patients are using pAF vs. placebo. A vertical and horizontal measure of defect in mm will be performed, and defect area calculated. A complete re-epithelialization (absence of a defect) is defined when the measures equal zero.
2. Pain will be measured through a 0-10 scale on days 1, 2, 3, 4, 5, 6, and 7. Participants will rate their peak pain at the end of each day and directly return the forms at their in-person visit on day 8 to the examiners. They will complete a separate survey for each eye.
3. Uncorrected visual acuity will be measured at post-operative day 8, months 1, 3, 6, and 12 by trained physicians.
4. Manifest refraction and best-corrected visual acuity will be measured at months 1, 3, 6, and 12 by trained physicians.
5. Ocular surface staining will be measured at post-operative months 1, 3, 6, and 12 using an area density index.²⁵ This is a published and validated index used to measure corneal staining. Corneal regularity will also be measured at months 1, 3, 6, and 12 with the Surface Regularity Index (SRI) obtained via Zeiss Atlas 9000 Corneal Topography™.

8 Other Medications

- Oral pain medications usage will be tracked for the first 7 days.

9 Patient Withdrawal From Study

- A subject may withdraw their consent at any time without affect to their care.

10 Discontinuation of Study Drug

The study drug will be discontinued if any of the following occur:

- Development of severe ocular infection.
- Any other condition that in the opinion of the treating physician and ophthalmologist are not compatible with participation in this study.

11 Discontinuation of Study

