3.2.2.1 Eligibility for Secondary Analysis

The secondary endpoint is to be evaluated in all PRK-treated eyes among consented and enrolled patients.

3.2.3 *Exploratory Endpoints*

Exploratory endpoints of the pAF after PRK trial, and the populations eligible for each tertiary analysis, include:

- i. Dimensions of epithelial defects as assessed on Days 1 to 8 except Day 2
- ii. Pain as assessed on 0-10 point scale on Days 1 to 7
- iii. Uncorrected visual acuity on Day 8 and at 1, 3, 6, and 12 Months
- iv. Best corrected visual acuity at 1, 3, 6, and 12 Months
- v. Ocular surface staining at 1, 3, 6, and 12 Months
- vi. Corneal Regularity via Surface Regularity Index (SRI) at 1, 3, 6, and 12 months

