11. SAFETY ANALYSES

11.1 Ocular Adverse Events

The primary safety analyses will be based on the as-treated population, defined as subjects who are randomized and receive at least one dose of study agent. Safety endpoints will include ocular adverse events, ophthalmic exam findings, and use of rescue treatments. The occurrence of ocular adverse events will be recorded from the time of randomization through the last study visit. AEs will be categorized by System Organ Class and Preferred Term using the Medical Dictionary for Regulatory Activities (MedDRA) and by severity using the Common Terminology Criteria for Adverse Events dictionary.

In general, all AE tables will be presented by treatment group, causality and severity. The following will be summarized and presented overall and by treatment group:

- The number and percentage of subjects experiencing an SAE
- The number and percentage of subjects experiencing an SAE by preferred term and by severity of event
- The number and percentage of subjects experiencing an SAE by preferred term and by relationship to study drug
- The number and percentage of subjects experiencing an AE
- The number and percentage of subjects experiencing an AE by preferred term and by severity of event
- The number and percentage of subjects experiencing an AE by preferred term and by relationship to study drug
- The number and percentage of AEs that cause a subject to discontinue study drug
- The number and percentage of AEs leading to death.

Adverse events will be coded using the Medical Dictionary for Regulatory Activities (MedDRA) central coding dictionary. Adverse events will be described in summary tables and in individual listings for the DSMB reports.

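### The SAP 11.2 count of best-corrected vision loss omits the Month 1 and Month 3 readings, so early transient loss that meets no listed adverse event is not counted as safety

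*SAP*

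**What the plan says.** Safety is the primary objective in both documents. Protocol 5.4 bases its evaluation on "scheduled eye examinations at days 1 (day of surgery) through 8 (in-person follow-up visit) and at months 1, 3, 6 and 12". SAP 11.1 sets out what is analysed: "Safety endpoints will include ocular adverse events, ophthalmic exam findings, and use of rescue treatments". Examination findings are thus a safety endpoint in their own right, alongside adverse events.

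The analysis of that endpoint is in SAP 11.2. It reports, by arm, participants with "loss of best corrected vision in either eye by one line or more" and repeats the count with eyes as the unit. The reference value and the visits follow in the same sentence of the SAP: "compared to best corrected vision prior to treatment, at 6-month and 1-year evaluations will be reported". No other visit is named, no test is specified and no reason is given for the choice of visits. Protocol 12.6, the protocol's own safety analysis section, adds no other examination summary.

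On data collection, Protocol section 7 states: "Manifest refraction and best-corrected visual acuity will be measured at months 1, 3, 6, and 12 by trained physicians". Treatment is short; Protocol section 5 describes dosing "for a total of 7 days of study drug administration". The SAP places the full set of BCVA readings among its exploratory efficacy endpoints (SAP 3.2.3): "Best corrected visual acuity at 1, 3, 6, and 12 Months".

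**The concern.** Exposure ends on Day 7, yet the first BCVA reading in the line-loss count is at Month 6. If pAF caused a temporary loss of corrected vision, Months 1 and 3 are the scheduled BCVA visits most likely to show it, and neither is in the count. A patient seen with a loss at Month 1 or 3 who leaves before Month 6 contributes nothing to the table either. SAP 8.2 keeps all available data from withdrawn subjects, but only through each outcome's own analysis strategy, and 11.2 makes no use of the earlier visits.

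At stake is whether the safety report of a trial with a safety primary objective shows how many patients in each arm temporarily lost corrected vision after treatment.

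**Working it through.** The documents attach no sample size, power or alpha to the 11.2 table, so there is no plan figure to reproduce. The check compares visit lists and then follows an early loss through each planned analysis.

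**Step 1: timing of the readings.** Inputs are the last dose on Day 7 (Protocol section 5 and the Schedule of Events) and the visit windows in the Schedule of Events. Days after last dose = study day − 7.

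| BCVA visit | Window (study day) | Days after last dose | In SAP 11.2? |
|---|---|---|---|
| Month 1 | 30 ± 10 = 20 to 40 | 13 to 33 | No |
| Month 3 | 90 ± 14 = 76 to 104 | 69 to 97 | No |
| Month 6 | 180 ± 30 = 150 to 210 | 143 to 203 | Yes |
| Month 12 | 365 ± 30 = 335 to 395 | 328 to 388 | Yes |

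The count uses 2 of 4 scheduled readings. The earliest one used comes about 20 to 29 weeks after the last dose (143/7 = 20.4; 203/7 = 29.0).

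**Step 2: what the AE tables would catch.** Protocol 6.1 restricts recording to the ocular events specified in 6.1.2. Several of these can be found at an early examination: infection, delayed healing, scarring or haze, corneal erosion. One is based on acuity: worse than 20/40, from 3 months on. To put that threshold on the scale of 11.2, use logMAR = log10(denominator/20), starting from the 20/20 potential required for eligibility:

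- 20/25: log10(25/20) = 0.097, about one line, the 11.2 threshold.
- 20/40: log10(40/20) = 0.301, about three lines.

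From a 20/20 baseline, the acuity-based event therefore needs a loss of more than about three lines and cannot apply at Month 1. The protocol does not say whether the 20/40 limit refers to corrected or uncorrected acuity.

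**Step 3: following each kind of loss.**

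| Loss of BCVA | Counted as safety? |
|---|---|
| Present at Month 6 or 12, one line or more | Yes, in 11.2 |
| Early, with haze, infection, erosion or another listed event | Yes, the listed event is in the AE tables |
| Month 3, acuity worse than 20/40 | Yes, in the AE tables (if the limit covers corrected acuity) |
| Month 1, gone by Month 6 or patient has left, no listed event | No |
| Month 3, about one to three lines, gone by Month 6 or patient has left, no listed event | No |

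**Step 4: whether the efficacy analysis fills the last two rows.** SAP 10.3.1 analyses acuity at other visits in the same way as the secondary outcome, that is, with a mixed model on log acuity. That compares means and does not count eyes that lost lines. An invented illustration shows the difference. Take 31 patients per arm (63/2, rounded down), with one line lost in both eyes by 4 pAF and 1 placebo patients at Month 1, all recovered by Month 6:

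- Line-loss count at Month 1: 4/31 = 13% against 1/31 = 3%.
- Line-loss count at Month 6: 0 against 0.
- Shift in mean acuity at Month 1: (4 − 1) × 0.1/31 = 0.01 logMAR.

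**The case against.** The strongest reply is that early data are not lost. SAP 11.2 is presented as an addition to the AE reporting, and the SAP attaches the term primary safety analyses to the AE tables in 11.1, which cover randomization to the last visit and are compared by arm. Protocol 12.1 plans descriptive statistics of vision by arm at each follow-up visit. SAP 3.2.3 and 10.3.1 compare acuity between arms at Months 1 and 3, and SAP 10.3.5 compares staining and surface regularity at all evaluation times. The DSMB may ask for further analyses. A reader might infer that early loss of vision never reaches the safety result, or that 11.2 alone answers the primary objective. The documents support neither reading.

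A second reply is that late visits suit a table aimed at lasting loss. Post-operative steroid drops continue to Day 90 in both arms, so Month 6 is the first scheduled visit clearly after them. That is a defensible purpose, though the SAP does not state it. Nor does 11.2 contradict Protocol 5.4, which says which examinations inform the evaluation and does not require a line-loss count at each.

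A third is that the size is unknown. The 4 against 1 split is invented and would give a two-sided Fisher p of about 0.35. No document gives a line-loss rate or attrition by visit; Protocol 12.5 and SAP section 6 expect only a small number lost. A claim that the count rests on the visits with the heaviest attrition therefore has no figure behind it.

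All of this stands, and it narrows the point. It does not close the last two rows of Step 3: none of the routes named counts those patients in a prespecified safety summary.

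**Conclusion.** The concern holds in limited form. The 11.2 count leaves out two of the four BCVA readings collected, the two nearest exposure. As a result, a loss at Month 1, or of about one to three lines at Month 3, that meets no listed event and either resolves by Month 6 or occurs in a patient who leaves before then, is not counted as safety. It would appear only within descriptive summaries and an exploratory comparison of means.

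This rests on two assumptions. The first is a baseline of about 20/20; from a better baseline, more than three lines could be lost before the 20/40 limit is passed. The second is that the list in Protocol 6.1.2 is exhaustive, as Protocol 6.1 indicates. Protocol 5.4 speaks of all ocular adverse events. If that wording governs, an investigator could record an early line loss as an event, but no threshold is set, so capture would depend on individual judgement.

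How many patients are affected cannot be estimated from the documents. This is a gap in safety reporting that is cheap to close. It does not undermine the AE analysis, the sample size or any hypothesis test.

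**What to change.** In SAP 11.2, report by arm the number and proportion of participants, and of eyes, with loss of one line or more of best-corrected vision from the pre-treatment value at Months 1, 3, 6 and 12. Add a row for such loss at any of these visits, so that patients who leave before Month 6 still contribute. Show the denominator at each visit: the Schedule of Events allows these visits to be done by telehealth or phone, so some BCVA readings may be missing.

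The cost is two more columns and one more row, from data already collected. The sample size and alpha do not change, because the table is descriptive. The drawback is that transient early losses to be expected after PRK itself will appear in both arms, so the early columns should be read against the randomised placebo arm. The Month 6 and Month 12 columns stay as the view of lasting loss.

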12. OTHER PLANNED EXPLORATORY ANALYSES

The discussion of exploratory analyses presented in this SAP is by no means exhaustive, as the pAF after PRK trials will generate data useful for exploratory analyses of clinical interest. We intend to use contemporary analytic approaches, including modification of existing approaches and derivation of novel techniques when appropriate, for such analyses. All exploratory, non-prespecified analyses will be clearly described as such in published reports. These exploratory analyses will be explicitly prespecified in advance, in separate Analysis Plans or in an updated version of this document as appropriate.

